4.3.4 Potential Effects of Pembrolizumab

Pembrolizumab toxicities are generally associated with the activation of autoreactive T-cells resulting in immune-related adverse events (irAEs) and embryofetal toxicity. The safety of pembrolizumab at 200 mg every 3 weeks or 400 mg every 6 weeks has been evaluated in multiple clinical studies, and the most common adverse drug reactions (ADRs) ($\geq 20\%$) were fatigue, diarrhea, and nausea. The majority of ADRs reported were of Grade 1 or 2 in severity. For detailed information regarding the safety of pembrolizumab administration please refer to the Food and Drug Administration (FDA)-approved package insert ([Keytruda \(pembrolizumab\) PI 2018](#)).

4.3.5 Potential Overlapping Toxicities

Nonclinical toxicology studies evaluating the combination of modakafusp alfa and pembrolizumab were not conducted and are not warranted per ICH S9 ([ICH 2018](#)). Pembrolizumab is a mAb that binds to the human PD-1 receptor and blocks the interaction of PD-1 with PD-L1/PD-L2.

Modakafusp alfa and pembrolizumab both activate the immune system, so known PD-1 immunotherapy-related toxicities (eg, pneumonitis, colitis, hepatitis, dermatitis, IRRs, endocrinopathies, and nephritis) observed following the administration of pembrolizumab may be enhanced when combined with modakafusp alfa. Details regarding the full safety profile of pembrolizumab can be found in the FDA-approved package insert ([Keytruda \(pembrolizumab\) PI 2018](#)). To minimize the risk to patients treated with modakafusp alfa and pembrolizumab, phase 2 will include a safety lead-in phase for the combination cohorts to determine the safety and tolerability of the combination doses and regimen. Pembrolizumab will be administered at the approved dose and schedule of 400 mg IV once every 6 weeks (Q6W) to maximize the possibility of observing clinical benefit.

The safety of the pembrolizumab and pegylated interferon alfa-2b (PEG-IFN) combination was studied in 2 phase 1/2 studies. Seventeen patients were enrolled in the Keynote-029 trial ([Atkins et al. 2018](#)), 5 with melanoma and 9 with renal cell carcinoma (RCC). Across dose levels, the most common treatment-related AEs of any grade were fatigue (n = 11, 65%), pyrexia (n = 7, 41%), chills, diarrhea and nausea (n = 6, 35% each). Grade 3 to 4 AEs were fatigue (n = 1), AST increase (n = 1), neutropenia (n = 1), and depression (n = 2). Forty-three patients with melanoma were enrolled in the Keynote-020 trial ([Davar et al. 2018](#)). The most frequent treatment-related toxicities were Grade 1 hyponatremia (11.1%), Grade 2 lymphopenia (10.8%), Grade 3 hyponatremia (10.3%), Grade 3 lymphopenia (12%) and Grade 3 fatigue (16.2%). Fifteen patients (34.9%) developed immune-related AEs (irAE) of any grade, including vitiligo (16.3%), hypothyroidism (16.3%), and one patient each with adrenal insufficiency (Grade 3), pneumonitis (Grade 4), and uveitis (Grade 4). No treatment-related deaths occurred.

4.3.6 Potential Pharmacokinetic Drug Interactions and Other Forms of Interaction

The potential for a direct PK drug-drug interaction between modakafusp alfa and pembrolizumab is likely low. Nevertheless, both pembrolizumab and modakafusp alfa are humanized IgG4 antibodies and, as such, potential ADA for modakafusp alfa generated against its IgG4 backbone may also impact the PK of pembrolizumab and vice versa. To assess the potential for immunogenicity drug-drug interaction between modakafusp alfa and pembrolizumab, serum PK of pembrolizumab when administered in combination with modakafusp alfa will be characterized in the study and compared with the reported pembrolizumab PK as monotherapy in solid tumor patients.

4.4 Rationale for the Proposed Study

4.4.1 General Rationale for Modakafusp Alfa in Solid Tumors

Pogue and colleagues previously indicated robust, complete antitumor responses in CD38-expressing, IFN α -sensitive xenograft models of MM following treatment with modakafusp alfa, driven by direct antiproliferative activity of IFN α and indirect activation of innate immune cell subtypes including M1 macrophage and NK cells ([Pogue et al. 2016](#)).

[figure not shown]
[REDACTED]

Figure 4.a

Figure 4.b

[Redacted]

[Redacted]

4.4.2

[Redacted]

[Redacted]

[REDACTED]

4.4.3 Rationale for Phase 2 Expansion Phase Cohorts

Once a RP2D is defined in Phase 1b, enrollment will begin into phase 2 assessing the following cohorts in combination with pembrolizumab. The combination cohorts, including patients in the safety-lead phase, will enroll patients with unresectable/metastatic melanoma in the following subgroups:

- I. Unresectable/metastatic cutaneous melanoma with primary resistance to no more than 2 prior lines of anti-PD1 containing treatments in the metastatic setting.
- II. Unresectable/metastatic cutaneous melanoma with acquired resistance to no more than 2 prior lines of anti-PD1 containing treatments in the metastatic setting.
- III. Unresectable/metastatic cutaneous melanoma naïve to prior anti-PD1 containing treatments in the metastatic setting.

In addition to the general rationale for modakafusp alfa in solid tumors presented in Section 4.4.1, rationales are presented in the indicated sections for patients with melanoma (Section 4.4.3.2) and for the combination with pembrolizumab [REDACTED]

Additional expansion arms exploring modakafusp alfa either as a single agent (SA) or as a combination may be added, based on information obtained during the dose-escalation or expansion phases.

4.4.3.1 [REDACTED]

[REDACTED]

4.4.3.2 *Rationale for Treatment of Melanoma Patients with Modakafusp Alfa In Combination with a CPI*

Immunotherapy with a checkpoint inhibitor (CPI) is safe and produces durable responses in 30% to 40% of patients with advanced melanoma (Larkin et al. 2015; Ribas et al. 2016). However, a significant portion of patients do not benefit from CPI treatment. For patients who progress after CPI, remaining options depend on the BRAF mutational status. A recent review of the published literature on CPI rechallenge indicated low response rates of 15% to 20% (Larkin et al. 2015; Ribas et al. 2016).

In addition to the general working hypothesis described in Sections 4.4.1 and 4.4.3.1, interest in the melanoma cohorts is supported by the work of Chen et al (Chen et al. 2018), which showed that CD38 expression is upregulated in preclinical NSCLC and melanoma tumor models after progression on CPI treatment and that this upregulation can be a mechanism of resistance to anti-PD-1/PD-L1 treatments. In vitro and in vivo studies demonstrate that CD38 inhibits CD8+ T-cell function via adenosine receptor signaling. The expression of CD38 in melanoma cancer cells may increase the targeting of modakafusp alfa to these resistant cells, providing additional opportunities for binding of attenuated IFN to IFNAR on these cancer cells. This mechanism of resistance to CPI has since been described in other tumor models.

Finally, exposure to modakafusp alfa increases PD-L1 expression in myeloma, and exposure to IFN α increases PD-L1 expression in human cancer, including melanoma.

Mechanism of resistance to CPI may be different in terms of acquired or primary resistance. Therefore 2 different expansion cohorts will assess modakafusp alfa and pembrolizumab in patients who initially responded or not to anti-PD-1 treatment (Blank et al. 2004; Iwai et al. 2002) (Vacchelli et al. 2015).

If the combination of modakafusp alfa and pembrolizumab is safe and a meaningful clinical activity is seen in melanoma, additional expansion cohorts assessing tumor types sharing the same rationale can be added.

5.0 STUDY OBJECTIVES AND ENDPOINTS

5.1 Objectives

5.1.1 Primary Objective

The primary objective is to determine the safety and tolerability of modakafusp alfa as a SA in patients with locally advanced or metastatic solid tumors (phase 1b) and in combination with pembrolizumab in unresectable/metastatic cutaneous melanoma (phase 2 safety lead-in) and to

evaluate the efficacy of modakafusp alfa in combination with pembrolizumab in patients with unresectable/metastatic cutaneous melanoma (phase 2 expansion).

5.1.2 Secondary Objectives

The secondary objectives are:

- To define the MTD and/or PAD of modakafusp alfa SA, if applicable (phase 1b).
- To select the RP2D of modakafusp alfa SA (phase 1b) and in combination with pembrolizumab (phase 2 safety lead-in).
- To evaluate modakafusp alfa PK as a SA (phase 1b) or in combination with pembrolizumab (phase 2 safety lead-in).
- To assess the preliminary antitumor activity of modakafusp alfa as a SA (phase 1b).
- To further characterize the antitumor effect of modakafusp alfa in combination with pembrolizumab based on immune Response Evaluation Criteria in Solid Tumors (iRECIST) in expansion cohort patients (phase 2 expansion).
- To evaluate safety and tolerability of modakafusp alfa in combination with pembrolizumab (phase 2 expansion).
- To characterize the immunogenicity of modakafusp alfa in patients with solid tumors (phase 1b and phase 2).

5.1.3 Exploratory/Additional Objectives

The exploratory/additional objectives are:

- To assess modakafusp alfa CD38 RO of peripheral immune cells in patients treated with modakafusp alfa as a SA (phase 1b) or in combination with pembrolizumab (phase 2).
- To explore predictive biomarkers of response (phase 1b and phase 2).
- To evaluate the effect of modakafusp alfa on QTcF intervals (phase 1b and phase 2 safety lead-in).
- To evaluate the relationship between administered dose and exposure of modakafusp alfa, RO of CD38, and IFN pathway induction as evaluated by gene expression changes and production of cytokines/chemokines (phase 1b and phase 2).
- To evaluate the relationship between evidence of IFN pathway induction (as described above) with evidence of activation of the innate and/or adaptive immune response as assessed by changes in immunophenotype and T-cell antigen receptor (TCR) clonality of peripheral blood and tumor (phase 1b and phase 2).
- To evaluate the relationship between modakafusp alfa exposure and/or CD38 RO with immune cell activation (as described above), and clinical response (phase 1b and phase 2).

- To evaluate correlations between baseline tumor IFN pathway gene expression with either the degree of IFN pathway induction or the level of immune cell activation on treatment (phase 1b and phase 2).
- To characterize germline DNA variants for correlations with clinical outcome, pharmacodynamic effects, and PK (phase 1b and phase 2).
- To further characterize the antitumor effect of modakafusp alfa based on changes in the tumor growth rate between the most immediate pretreatment period and on treatment (phase 1b and phase 2).
- To characterize serum PK of pembrolizumab when administered in combination with modakafusp alfa (phase 2).
- To assess the Type I interferon (IFN) gene expression signature in peripheral blood (phase 1b and phase 2).
- To evaluate correlations with clinical outcome with either the on-treatment immunophenotype of the tumor microenvironment or changes in the immunophenotype from baseline (phase 2).

5.2 Endpoints

5.2.1 Primary Endpoints

The primary endpoints are:

- Frequency and severity of TEAEs according to the National Cancer Institute Common Terminology Criteria for Adverse Events, Version 5 (NCI CTCAE v5) (phase 1b and phase 2 safety lead-in).
- Number of patients with DLTs (phase 1b and phase 2 safety-lead in).
- Number/percentage of patients with 1 or more SAEs (phase 1b and phase 2 safety-lead in).
- Number/percentage of patients with 1 or more TEAE leading to dose modification and/or treatment discontinuation (phase 1b and phase 2 safety-lead in).
- Overall response rate (ORR) (complete response [CR] + partial response [PR]) assessed according to Response Evaluation Criteria in Solid Tumors, Version 1.1 (RECIST v1.1) for melanoma patients (phase 2 expansion).

5.2.2 Secondary Endpoints

- MTD or PAD (as defined in 6.1.1), if available (phase 1b).
- RP2D for SA and in combination with pembrolizumab, respectively (phase 1b and phase 2 safety lead-in).
- Frequency and severity of TEAEs according to the NCI CTCAE v5 (phase 2 expansion).

- Number/percentage of patients with 1 or more SAEs (phase 2 expansion).
- Number/percentage of patients with 1 or more TEAE leading to dose modification and/or treatment discontinuation (phase 2 expansion).
- PK parameters after the first dose of modakafusp alfa on Cycle 1 Day 1 (C1D1) and on Cycle 2 Day 1 (C2D1) for dose escalation phase (phase 1b) and on Cycle 1 Day 1 (C1D1) and Cycle 3 Day 1 (C3D1) for the phase 2 safety lead-in phase of dose expansion:
 - Maximum observed concentration (C_{max}).
 - Time of first occurrence of C_{max} (t_{max}).
 - Area under the plasma concentration versus time curve from time 0 to time t (AUC_t).
 - Area under the concentration-time curve from time 0 to infinity (AUC_{∞}).
 - Terminal disposition phase half-life ($t_{1/2z}$).
 - Clearance.
 - Volume of distribution at steady state (V_{ss}).
- ORR (CR + PR) assessed according to the RECIST v1.1 for patients in dose escalation (phase 1b).
- Disease control rate (DCR) (CR + PR + stable disease [SD]) (phase 1b and phase 2).
- DOR (phase 1b and phase 2).
- TTP (phase 1b and phase 2).
- Progression-free survival (PFS) assessed according to RECIST v1.1 (phase 1b and phase 2)
- OS (phase 1b and phase 2).
- Efficacy measures of ORR, DCR, DOR, TTP, and PFS based on iRECIST (phase 2 expansion).
- Anti-modakafusp alfa antibody incidence and titer (phase 1b and phase 2).

Definitions and timeframes of primary and secondary endpoints are provided in Section 6.3.3.

5.2.3 Additional/Exploratory Endpoints

The exploratory endpoints are:

- Tumor mutations characterized from cell-free DNA (cfDNA) and quantification of circulating tumor cells (CTCs) will be evaluated at baseline and assessed for correlations with clinical response.
- Genomic and protein expression of baseline tumor tissue.
- Germline mutations and polymorphisms as assessed by whole exome sequencing of peripheral blood.

- Change of QTcF interval using data from PK time matched triplicated electrocardiogram (ECG) readings.
- Induction of modakafusp alfa–induced gene expression changes, including type I IFN signature, assessed in peripheral blood and tumor.
- Fold-change in plasma levels of IP-10 and other cytokines/chemokines.
- Immune cell activation as assessed in peripheral blood and tumor by (a) immunophenotypic changes and (b) evaluation of TCR diversity.
- Modakafusp alfa antitumor effect size based on observed change in tumor growth rate using prescreening, screening, and on-treatment diagnostic imaging, as available.
- Serum PK of pembrolizumab when administered in combination with modakafusp alfa.
- Cellular CD38 RO of peripheral blood assessed at time points surrounding the first and second modakafusp alfa SA administrations (phase 1b) and at time points surrounding the first and third modakafusp alfa administrations when in combination with pembrolizumab (phase 2).
- Modakafusp alfa–induced Type I IFN gene expression signature in the peripheral blood (phase 1b and phase 2).
- Immunophenotypic evaluations of the tumor and tumor microenvironment utilizing multiplexed immunohistochemistry or similar methodologies.

[figure not shown]
6.0 STUDY DESIGN

6.1 Overview of Study Design

This is an open-label, phase 1b/2 study designed to evaluate the safety, tolerability, pharmacokinetics (PK), pharmacodynamics and antitumor response of modakafusp alfa as a SA and in combination with pembrolizumab in patients with advanced or metastatic solid tumors. Please see Section 7.0 for complete eligibility criteria.

The study consists of 2 phases as shown in Figure 6.a.

Figure 6.a Study Schema

RP2D: recommended phase 2 dose; SA: single agent.

6.1.1 Phase 1b Single-Agent Dose Escalation

Phase 1b will enroll patients with advanced/metastatic solid tumors that have no standard therapeutic option, are intolerant to those therapies, or have refused them.

The modakafusp alfa SA dose escalation phase is designed to determine the SA RP2D and schedule of modakafusp alfa for further testing. The single-agent RP2D may be either the MTD based on DLTs or a PAD defined by the PK/pharmacodynamic model or exposure-response (ER) analysis in place.

A minimum of 3 patients will be enrolled in the starting dose cohort of modakafusp alfa 0.1 mg/kg administered Q3W. Doses will be escalated as follows: 0.1, 0.2, 0.4, 0.75, 1.5, 3 and 6 mg/kg. Patients will be assessed for DLTs until Cycle 2 Day 1 (C2D1) can be administered from a safety

standpoint. If there are no DLTs in the first cohort of 3 evaluable patients dosed at 0.1 mg/kg, Bayesian Logistic Regression Model (BLRM) guided by the Escalation with Overdose Control (EWOC) principle will be used in successive dose escalation cohorts to estimate the next dose level. More conservative dose escalation, evaluation of intermediate doses, and expansion of an existing dose level are all permissible following discussions between the sponsor and the investigators, if such measures are needed for patient safety or for a better understanding of the dose-related toxicity, exposure, or pharmacodynamics. It is estimated that approximately 30 patients will be enrolled until either the MTD and/or PAD is identified.

6.1.2 Phase 2 Dose Expansion

Enrollment into phase 2 expansion in combination with pembrolizumab will be initiated once the RP2D of modakafusp alfa has been determined in phase 1b.

The combination treatment cohorts will begin with a single safety-lead in period to evaluate safety and tolerability during the Cycle 1 DLT evaluation period of modakafusp alfa with pembrolizumab. If there are no DLTs in the first 3 patients during Cycle 1 of the safety lead-in period with modakafusp alfa SA RP2D in combination with pembrolizumab 400 mg Q6W, the combination dose and regimen could be selected for the 3 disease cohorts described below. If there is 1 DLT in the initial 3 patients in the safety-lead in period, an additional 3 patients will be enrolled at the same modakafusp alfa RP2D in combination with pembrolizumab 400 mg Q6W. If there are ≥ 2 DLTs in the first 3 patients at the modakafusp alfa SA RP2D, enrollment will resume at the next lower dose level of modakafusp alfa RP2D in combination with pembrolizumab. Other approved pembrolizumab dosing regimens (eg, 200 mg Q3W) could be tested in the safety-lead in period if 400 mg Q6W in combination with modakafusp alfa at one dose lower than RP2D is intolerable.

For the safety lead-in period, patient enrollment will be staggered between the first and second patients by 7 days. The second and third patients can be dosed concurrently if the first patient in the cohort has gone through the Day 8 visit without clinically significant acute toxicities. Patients enrolled in the safety lead-in phase could have any of the 3 melanoma disease categories described below.

Following completion of the safety lead-in phase and review of safety data, phase 2 of the study will further explore the safety and efficacy of modakafusp alfa treatment in combination with pembrolizumab. The combination cohorts, including patients in the safety-lead phase, will enroll patients with unresectable/metastatic melanoma in the following subgroups:

- I. Unresectable/metastatic cutaneous melanoma with primary resistance to no more than 2 prior lines of anti-PD1 containing treatments in the metastatic setting.
- II. Unresectable/metastatic cutaneous melanoma with acquired resistance to no more than 2 prior lines of anti-PD1 containing treatments in the metastatic setting.
- III. Unresectable/metastatic cutaneous melanoma naïve to prior anti-PD1 containing treatments in the metastatic setting.

Up to 25 patients will be enrolled in each of the 3 cohorts in phase 2. A Bayesian predictive probability design will be used to allow multiple futility analyses for early termination due to futility.

If modakafusp alfa in combination with pembrolizumab is safe and meaningful clinical activity is seen, additional expansion cohorts may be added to assess other tumor types.

6.2 Number of Patients

It is expected that approximately 30 patients will be enrolled in the phase 1b dose escalation phase at approximately 3 to 4 sites. Up to 25 patients will be enrolled in each of the 3 combination therapy cohorts. A Bayesian predictive probability design was used to allow multiple interim analyses for early termination due to futility. Assuming 3 to 9 safety lead-in patients, the total sample size for phase 2 can be up to 84 patients.

The study is expected to enroll up to 114 patients overall.

6.3 Duration of Study

6.3.1 Duration of an Individual Patient's Study Participation

Patients may receive modakafusp alfa as a SA for up to 1 year or in combination with pembrolizumab for up to 2 years. Patients with demonstrated clinical benefit can continue treatment beyond those points if approved by the sponsor. These patients can continue receiving treatment in this study or in any of the poststudy access modalities described in the protocol (Section 6.3.5). Patients may discontinue treatment when they meet any of the discontinuation criteria stated in the protocol (Section 9.6).

All patients will have an EOT visit 30 days (+10 days) after receiving the last dose of study drug or before the start of subsequent systemic anticancer therapy, whichever occurs first, to permit detection of any delayed TEAEs and to resolve any ongoing events. Patients with unresolved TEAEs will continue the periodic safety follow-up until complete resolution or stabilization (established as sequelae) occurs.

Patients who discontinue study treatment for reasons other than progressive disease (PD) will continue PFS follow-up every 12 ± 1 weeks from the EOT visit until the occurrence of PD, lost to follow-up, consent withdrawal, death, start of subsequent systemic anticancer therapy, or study termination, whichever occurs first. After disease progression or starting another systemic anticancer therapy, all patients will be followed every 12 ± 1 weeks for OS until death or study termination.

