AE reporting	Recorded from signing of the ICF through 30 days after last dose of study drug or the start of subsequent anticancer therapy, whichever occurs first.						
	SAEs will be reported from signing of ICF through 30 days after last dose of study drug even if the patient starts nonprotocol systemic therapy.					Only study drug-related SAEs will be reported.	
Dosing							
Modakafusp alfa infusion ^d	X	X	X				
Disease Assessment							
CT/MRI scans ^e	Repeat every 6 weeks through Cycle 6 then every 9 weeks thereafter.					X	

Table 16.c Schedule of Events, Continued: Cycle 7 Through EOT and Follow-up (Phase 1 Dose Escalation)

Study Period or Treatment Cycle	Cycles 7, 10, 13, and 16+	Cycles 8, 11, 12, and 14	Cycle 9 and Cycle 15		EOT	Follow-up	
			Day 1	Day 2		PFS ^s	OS ^t
Day	Day 1	Day 1	Day 1	Day 2	30 (+10) Days After Last Dose or Before Start of Subsequent Systemic Anticancer Therapy, Whichever Occurs First	Q12W	
Window Allowed	±4 d	±4 d	±4 d	0		±1 week	
Laboratory Assessments							
Chemistry ^f	X	X	X				
Hematology ^h	X	X	X				
Pregnancy test ^k	X	X	X		X		
Serum sample for modakafusp alfa PK ^m	Please refer to Table 16.f below.						
Blood sample for mass cytometry (immunoprofiling) ⁿ			X ^o	X	X		
Serum sample for circulating biomarkers ^d			X ^p	X	X		
Serum sample for immunogenicity (ADA) ^{d,q}	X	X	X		X		
Blood sample for RNA			X ^o	X	X		
Blood sample for receptor sequencing			X ^o				
OS Follow-up							
Survival							X
Subsequent therapy						X	

ADA: antidrug antibody; AE: adverse event; CxDx: Cycle x Day x; cfDNA, cell-free DNA; CT: computed tomography; d: day(s); ECG: electrocardiogram; ECOG: Eastern Cooperative Oncology Group; EOT: end of treatment; ICF: informed consent form; IRR: infusion-related reaction; RECIST: Response Evaluation Criteria in Solid Tumors; MRI: magnetic resonance imaging; OS: overall survival; PD: progressive disease; PFS: progression-free survival; PK: pharmacokinetic(s); Q3W: once every 3 weeks; Q12W: once every 12 weeks; QTc: corrected QT interval; RBC: red blood cell; SAE: serious adverse event; SOE: Schedule of Events; TBNK: quantification of T cells (including CD4+ and CD8+ T cells), B cells, and natural killer cells; TSH: thyroid stimulating hormone; WBC: white blood cell.

Crosses in parentheses “(X)” indicate tests are to be performed only under certain circumstances as indicated in associated footnote(s).

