Monitoring of concomitant medication and procedures	Recorded from signing of the ICF through 30 days after last dose of study drug or the start of subsequent anticancer therapy, whichever occurs first. The reporting period for irAEs is extended to 90 days after administration of the last dose of study drug or the start of subsequent anticancer therapy, whichever occurs first, and recorded in the eCRFs.					
AE reporting	Recorded from signing of the ICF through 30 days after last dose of study drug or the start of subsequent anticancer therapy, whichever occurs first.					
	SAEs will be reported from signing of ICF through 30 days after last dose of study drug even if the patient starts nonprotocol systemic therapy. Serious irAEs will be reported through 90 days after last dose of study drug.				Only study drug-related SAEs will be reported.	
Dosing						
Modakafusp alfa infusion ^d	X	X				
Pembrolizumab infusion ^e	(X)	X				
Disease Assessment						
CT/MRI scans ^f	Repeat every 6 weeks through Cycle 6 then every 9 weeks thereafter.				X	

CONFIDENTIAL

Table 16.e Schedule of Events, Continued: Cycle 4 Through EOT and Follow-up (Phase 2 Dose Expansion)

Study Period or Treatment Cycle	Cycles 4, 5, 6, 8, 9, 10, 11, 12, 13, 14, and 16+	Cycle 7 and Cycle 15		EOT	Follow-up	
		Day 1	Day 2		30 (+10) Days After Last Dose or Before Start of Subsequent Systemic Anticancer Therapy, Whichever Occurs First	PFS ^t
Day	Day 1	Day 1	Day 2	30 (+10) Days After Last Dose or Before Start of Subsequent Systemic Anticancer Therapy, Whichever Occurs First	Q12W	
Window Allowed	±4 d	±4 d	0	30 (+10) Days After Last Dose or Before Start of Subsequent Systemic Anticancer Therapy, Whichever Occurs First	±1 week	
Laboratory Assessments						
Chemistry ^g	X	X				
Hematology ^h	X	X				
Urinalysis ^j	X	X		X		
Pregnancy test ^k	(X)	(X)		(X)		
Immunosafety markers ^l	(X)	X		X		
Serum sample for modakafusp alfa PK ⁿ	Please refer to Table 16.g and Table 16.h below.					
Serum sample for pembrolizumab PK ⁿ	Please refer to Table 16.g and Table 16.h below.					
Blood sample for immunophenotyping ^o		X ^p	X	X		
Serum sample for circulating biomarkers ^d		X ^q	X	X		
Serum sample for immunogenicity (ADA) ^{d,r}	X	X		X		
Blood sample for RNA		X ^p	X	X		
Blood sample for receptor sequencing		X ^p				
OS Follow-up						
Survival						X
Subsequent therapy					X	

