7.12.2 Clinical Laboratory Evaluations

For the purposes of summarization in both the tables and listings, all laboratory values will be converted to standardized units. If a lab value is reported using a non-numeric qualifier (eg, less than (<) a certain value, or greater than (>) a certain value), the given numeric value will be used in the summary statistics, ignoring the non-numeric qualifier.

If a patient has repeated laboratory values for a given time point, the value from the last evaluation will be used. Laboratory test results will be summarized according to the scheduled sample collection time point. Change from baseline will be presented. Scheduled laboratory along with unscheduled lab test results will be listed.

Lab parameters to be analyzed are as follows:

- Hematology: hemoglobin, hematocrit, activated partial thromboplastin time (aPTT), platelet count, white blood cell (WBC) count, WBC differential (basophils, eosinophils, lymphocytes, monocytes, neutrophils), prothrombin time (PT)
- Chemistry: albumin, alanine aminotransferase (ALT), alkaline phosphatase, aspartate aminotransferase (AST), bilirubin (total), blood urea nitrogen, calcium, chloride, creatinine, glucose (non-fasting), HCO₃ or CO₂, LDH, phosphate, potassium, sodium, standard C-reactive protein, urate or uric acid

- Urinalysis: protein, glucose, nitrite, occult blood, specific gravity, pH, bilirubin, ketones, turbidity and color, leukocytes, urobilinogen
- Immunosafety markers: thyroid-stimulating hormone (TSH), free thyroxine (T4), cortisol (morning preferred)

If GFR is to be estimated, the MDRD or CKD-EPI equations shall be used. References are specified in Section 9.3.13.1 of Protocol Amendment 3.

Whenever available, laboratory values will be assigned toxicity grades using the NCI CTCAE version 5.0 or higher. Shift tables from baseline to the worst values will be constructed for laboratory parameters. Individual platelet and absolute neutrophil count (ANC) profiles will be generated for each dose level. Mean values over time for platelets and ANC will be produced for each phase as appropriate.

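### No chemistry or hematology is scheduled at the EOT visit meant to detect delayed events, and PFS follow-up patients have no scheduled contact between EOT and Day 90, when irAE reporting closes

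*Protocol*

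**What the plan says.** Protocol Section 6.3.1 states: "All patients will have an EOT visit 30 days (+10 days) after receiving the last dose of study drug", or sooner if another systemic anticancer therapy starts, and gives the purpose as "to permit detection of any delayed TEAEs and to resolve any ongoing events". Section 9.3.13.1 leaves the timing of chemistry and hematology to Appendix A, and Section 9.5 does the same for EOT procedures.

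In Appendix A, the phase 1b rows of Table 16.c read "Chemistry ^f X X X" and "Hematology ^h X X X". The three marks are the cycle Day 1 columns. The phase 2 chemistry row of Table 16.e reads "Chemistry ^g X X", again Day 1 only, and its hematology row follows the same pattern.

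For immune-related events, Section 10.3 and Table 16.d say: "The reporting period for irAEs is extended to 90 days after administration of the last dose of study drug". Patients who stop for reasons other than progression "will continue PFS follow-up every 12 ± 1 weeks from the EOT visit". After progression or a new therapy, OS follow-up runs every 12 ± 1 weeks, with no stated starting point.

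SAP Section 7.12.2 says: "Shift tables from baseline to the worst values will be constructed for laboratory parameters". SAP Section 7.12.1 ends the treatment-emergent period 30 days after the last dose.

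**The concern.** The visit has a stated safety purpose, but the tests most likely to show delayed toxicity of this drug are not on its list. Protocol Section 4.3.3 reports, among the first 17 patients, thrombocytopenia in 5 (29.4%), neutropenia in 3 (17.6%, all Grade 3 or higher) and one related ALT increase. Hepatitis and nephritis are pembrolizumab AESIs (Section 10.2.1.2). A laboratory change after the final dose in a patient without symptoms would be found only if someone happened to draw blood. A worst-value shift table cannot show a value that was never drawn.

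The second issue has the same form. The protocol asks for irAEs to Day 90, but in PFS follow-up it schedules no occasion between EOT and Day 90 on which anyone asks about them. Frequency and severity of TEAEs is a primary endpoint in phase 1b and the safety lead-in, so complete safety collection matters here.

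**Working it through.** **1. The EOT column, row by row.**

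| Row | Table 16.c (phase 1b) | Table 16.e (phase 2) |
|---|---|---|
| Chemistry | blank | blank |
| Hematology | blank | blank |
| Vital signs, physical examination, ECOG | blank | blank |
| 12-lead ECG | marked | marked |
| Pregnancy test | marked | marked (conditional) |
| ADA, circulating biomarkers, RNA | marked | marked |
| Urinalysis | no row | marked |
| TSH, free T4, cortisol | no row | marked |

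Other rows carry EOT marks, so the blanks are specific to these tests. The chemistry and hematology footnotes add nothing at EOT. Amendment 5 added urinalysis to the EOT visit, so that column has been revised while these rows stayed blank.

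**2. Who is left without a result.** Day 8 and Day 15 chemistry and hematology exist only in phase 1b Cycles 1 and 2 (Table 16.a) and phase 2 Cycles 1 and 3 (Table 16.d). In every other cycle the only scheduled draw is on Day 1. Section 8.6.2 requires neutrophil and platelet counts before a new cycle. Section 8.6.3.1 asks for at least weekly laboratory re-evaluation while modakafusp alfa is withheld for toxicity. The gap is therefore the patient whose last dose falls in another cycle and who reaches neither of these. Example: in phase 2 the first scan is due in the 7 days up to Cycle 3 Day 1. A patient taken off treatment at that scan, without a Day 1 check, had the last dose in Cycle 2, which has Day 1 laboratory tests only.

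**3. Timing of the first PFS follow-up.** Inputs: EOT on Day 30 to 40 after last dose; follow-up 12 ± 1 weeks later, so 11 × 7 = 77 to 13 × 7 = 91 days.

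- Earliest: 30 + 77 = Day 107, which is 107 − 90 = 17 days after the irAE window closes.
- Latest: 40 + 91 = Day 131, which is 131 − 90 = 41 days after.
- Unscheduled stretch from EOT to Day 90: 90 − 40 = 50 to 90 − 30 = 60 days.

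**4. OS follow-up.** If the clock runs from EOT, the result is the same as in step 3. If it runs from the last dose (an assumption), the contact falls on Day 77 to 91. The documents do not say which.

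**5. Where the 90-day rule appears.** Section 10.3 and the AE row of Table 16.d agree on 90 days for irAEs. Table 16.e has that sentence in the concomitant-medication row, and its nonserious AE line stops at 30 days. Its SAE line does carry 90 days for serious irAEs.

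**6. What the SAP would show.** The shift tables are not limited to 30 days, so an EOT laboratory value would enter them. The TEAE tables are limited: an irAE starting on Day 31-90 would not appear there, whether or not it was collected.

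**The case against.** The strongest reply is that most late toxicity is already covered. Laboratory tests are directed when dosing is delayed or held. Unresolved TEAEs and SAEs are followed past EOT. Suspected pembrolizumab events are worked up with laboratory tests (Section 8.10.3). The SAP lists unscheduled results and does not confine the shift tables to scheduled draws. At the January 2021 cutoff the median was 2 cycles, which in phase 1b carry Day 8 and 15 tests, and no patient had stopped for thrombocytopenia or neutropenia.

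This stands for patients with a recognised problem, and for those who stop in the early cycles. It does not reach patients who stop for progression without a recognised toxicity. Progression was the main reason for stopping at that cutoff (75.0% of treatment discontinuations).

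A reader might infer more than the documents support:

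- That there is no contact at all from Day 31 to 90. EOT itself may fall on Day 31-40, and OS contact could fall on Day 77-91 if counted from the last dose. An EOT brought forward to Day 13 or earlier would put a 77-day interval at or before Day 90 (13 + 77 = 90), but that happens only when new therapy starts, which ends PFS follow-up and closes the nonserious irAE window.
- That immune toxicity goes unmeasured. Phase 2 has TSH, free T4, cortisol and urinalysis at EOT. An irAE with onset before Day 90 can still be recorded at a later contact, and related SAEs stay reportable after that.
- That last-cycle laboratory effects are never measured. Step 2 shows that many patients would have a result.
- That a Day 90 contact would correct the TEAE tables. It would not, because they end at 30 days.

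**Conclusion.** The concern holds in a limited form. Chemistry, hematology and vital signs are missing from a visit whose stated purpose needs them, in both phases, and nothing elsewhere in the protocol supplies them. For the subgroup defined in step 2, the number of scheduled blood counts and liver or renal results after the last dose is zero. The size of that subgroup cannot be derived from the documents, so the shift tables can miss last-cycle toxicity by an amount that cannot be stated.

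The Day 107-131 result applies to PFS follow-up patients with EOT on Day 30-40. For OS follow-up patients the timing is undefined. The row placement in Table 16.e conflicts with Section 10.3 and Table 16.d. It is an editorial fault, but sites work from the schedule tables. All of this concerns collection and should be corrected. It does not affect the efficacy design.

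**What to change.** 1. Mark chemistry, hematology and vital signs at EOT in Tables 16.c and 16.e.
2. In Table 16.e, move the 90-day irAE sentence from the concomitant-medication row to the AE row, so that it agrees with Section 10.3 and Table 16.d.
3. Add a telephone irAE check at about Day 90 after the last dose for phase 2 patients in PFS or OS follow-up. Leave the PFS follow-up visits where they are: they carry CT/MRI, and moving the first one would shift post-treatment imaging. State the starting point of the OS follow-up clock.
4. In the SAP, add a listing or table for irAEs with onset on Day 31-90, since the TEAE tables will not contain them.

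The cost is two local tubes at a visit that already draws blood, a set of vital signs, one telephone call per phase 2 patient and one further output.
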